19.0 Resources Available

19.1 Resources Available: Resources Available: Feasibility of subjects is dependent on the number of individuals undergoing ECMO treatment and able to provide consent. This is a pilot study.

- Research space and software is available at the University of Minnesota, Division of Physical Therapy. Data collection will be completed at Fairview, East Bank Hospital.
- All research support staff have been trained on the protocol, completed regulatory HIPAA and CITI training.

Project Proposal: 11/28/16

**The Impact of Lower Extremity Weight-Bearing Leg Exercise
During the Pre-Ambulation Phase of Individuals Undergoing
Extracorporeal Membrane Oxygenation (ECMO)**

Principal Investigator: [name], PT, DPT, University of Minnesota

Co- Investigator: [name], PT, DPT, University of Minnesota Medical
Center, Fairview

Project Summary

Patients undergoing extracorporeal membrane oxygenation (ECMO) are at high risk for deconditioning and functional decline. Current research provides support for early mobilization of patients undergoing ECMO, and indicates that activity in this population is safe and feasible. The timeframe prior to mobilization depends on a number of factors, and can range significantly between different patient groups. One such factor is strength.

While active lower extremity exercise is common in the pre-ambulation phase of those receiving ECMO, the type of exercise selected varies and little is known about the benefit of weight-bearing closed chain exercise during this pre-ambulatory period. In order to evaluate this specific form of exercise, we will compare outcomes of patients who complete lower extremity exercise without loading to those who complete loaded exercises.

All participants in this study will progress through pre-existing Ambulatory ECMO Guidelines, established and currently in use at the University of Minnesota Medical Center, Fairview. Participants will be randomized into either group A or B. Group A will receive specific closed chain lower extremity squat exercises via the MOVEO XP Mobile Hi-Lo Platform System. MOVEO is an exercise leg press device. The MOVEO exercises will be added during parts C and D of the ECMO Early Mobilization Protocol listed below. Group B will progress through the ECMO Early Mobilization Protocol without the addition leg exercises on the MOVEO.

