Collecting and analyzing data on weight-bearing lower extremity exercise in this patient population will allow us to obtain important information on ways to address weakness associated with ECMO treatment, particularly in those who are unable to engage in bipedal ambulation.

[figure not shown]
MOVEO XP Mobile Hi-Lo Platform System

Company Website:

<http://www.djoglobal.com/products/charlottesville/moveo-xp>

ECMO Early Mobilization Protocol:

1. **Readiness for Mobility Assessment and Protocol** (Developed by ECMO therapy specialists at the University of Minnesota Medical Center)
 - a. Passive range of motion (PROM) and monitor for appropriateness of entering into the mobility program
 - b. Utilization of lift equipment to sit patient at the edge of the bed or into chair to promote wakefulness, when on minimal amounts or no sedation
 - c. Patient demonstrates the ability to follow 3/3 one-step commands
 - d. Patient tolerates 5 minutes of lower extremity ergometer, or performs ten reps of 3 active ROM of motion exercises involving the lower extremities
 - e. Sit at bedside unsupported for 5 minutes
 - f. Sit->stand and pre-gait activities (weight shifting, walking in place, etc.) directed by therapist
 - g. Bed->chair transfers (stand-pivot or squat-pivot)
 - h. Walking over ground with utilization of the mobility carts

The primary aim of this study is to assess the functional impact of leg exercise during the pre-ambulation phase in patients undergoing ECMO. Outcome measures will be categorized as either functional or hospital based. Hospital measures include: Hospital days, intensive care unit days, days on ECMO, days on mechanical ventilation, length of time from physical therapy evaluation to initial ambulation, and discharge disposition. Functional outcome measures include: Leg strength, grip strength, 30-second sit to stand test, Functional Status Score for the Intensive Care Unit (FSS-ICU), and the Richmond Agitation and Sedation Scale (RASS).

Background & Significance

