Aim 1: To determine if closed-chain leg exercise decreases the time to initial ambulation. *We hypothesize* that adding leg exercise will decrease time to ambulation.

Aim 2: To determine the impact of closed chain leg exercise on functional ability. *We hypothesize* that adding leg exercise will improve functional outcomes when added to an existing early mobilization program.

Aim 3: To determine the effect of closed chain leg exercise on hospital outcomes. *We hypothesize* that hospital related outcomes will improve when leg exercise is added to an existing early mobilization program.

Research Design & Methods

This initial pilot study will be conducted at the University of Minnesota Medical Center (UMMC), Fairview, and will involve 10 participants in each of the two groups (A and B). To account for attrition, 24 total subjects will be recruited; 12 per group. Approximately 3-5 patients are admitted to UMMC each month who are undergoing ECMO and could be considered for study inclusion. The study will be conducted with a goal endpoint of 1-year. Men and women aged 18-70 years old with refractory respiratory failure who are undergoing ECMO will participate over the duration of their ECMO treatment and hospitalization.

Recruitment and Consent

Standard practice includes a physician order for inpatient physical therapy for all individuals undergoing ECMO, as well as initial medical sedation. Most of those receiving ECMO are at least partially medically sedated at the time of physical therapy initiation. Only physical therapists who are specialty-trained ICU therapists and who are a part of this project will be working with this group of patients.

Any individual who meets inclusion criteria will be considered for participation, pending their ability to follow 3/3 one-step commands, as is outlined in the ECMO Mobility Protocol listed previously. Patients will be able to self-consent once sedation is reduced. After consent, individuals will be placed into either Group A or B and progress through the protocol. Group assignments will be determined based on 24 subjects, with the number 24 put into a random letter sequence generator prior to subject recruitment.

Inclusion Criteria

- Men and women 18-70 years old with refractory respiratory failure undergoing ECMO at the University of Minnesota Medical Center, Fairview.
- Able to follow 3 out of 3 one-step commands via protocol.
- Active Inpatient Physical Therapy Referral.

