 - Richmond Agitation and Sedation Scale (RASS), as completed in medical record by primary nurse
 - Functional Status Score for the Intensive Care Unit (FSS-ICU)
- Hospital Outcomes (data extraction from medical record)
 - Hospital days
 - Intensive care unit days
 - Days on ECMO
 - Days on mechanical ventilation
 - Length of time from physical therapy evaluation to initial ambulation
 - Discharge disposition- assigned a number for statistical analysis
 - Home (1)
 - Home with assistance (2)
 - Home with home therapy (3)
 - Home with outpatient therapy (4)
 - Transitional Care Unit (5)
 - Acute Inpatient Rehabilitation (6)
 - Long-term acute care hospital (7)
 - Long-term care setting (8)
 - Transfer to outside hospital (9)
- Physiological Monitoring: Monitoring physical therapists have extensive experience in mobilizing patients in the ICU, including those with arterial lines and on ventilation, as is standard practice for ICU therapy.
 - Respiratory rate (RR) via Drager Ventilators
 - Evita Series or Infinity Series
 - Oxygen (SpO2) and heart rate (HR)
 - Spacelabs Ultraview SL2700 (regular monitor)
 - Spacelabs Ultraview SL (portable monitor)
 - Blood Pressure (BP) via manual cuff or arterial line
 - Spacelabs Ultraview SL2700 or SL

Statistical Considerations

Physiological data (HR, BP, O2, RR) will be recorded throughout the study and analyzed between Groups A and B. Functional and Hospital outcomes will be analyzed to compare group differences at each of the data collection days (0, 5, 10, 15, 20, 30, 45, day of discharge).

Data will be analyzed at the University of Minnesota using the Statistical Package for Social Sciences (SPSS) software program. Test for normality will be completed via a paired t-test for parametric data and via Wilcoxon Rank Sum Test for non-parametric data.

Aim 1: Leg exercise on the Moveo will decrease time to initial ambulation.

- A paired t-test will be used to evaluate time to ambulation in Group A as compared to Group B.

Aim 2: Leg exercise on the Moveo will improve functional outcomes.

- There are 2 primary factors to assess, Group A and B, as well as the impact across time. To assess both factors, repeated measures ANOVA will be used.

Aim 3: Leg exercise on the Moveo will improve hospital outcomes.

- All hospital outcomes, except for discharge disposition, can be assessed between Group A and Group B by a paired t-test.
- Discharge disposition, categorical data, will be analyzed via Chi-Square test.

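### Aim 1 and the numeric Aim 3 outcomes compare two unmatched randomised groups with a paired t-test

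*Combined protocol and SAP*

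**What the plan says.** **Design.** The Project Summary states: "Participants will be randomized into either group A or B". Under Recruitment and Consent the allocation comes from a single list: "Group assignments will be determined based on 24 subjects, with the number 24 put into a random letter sequence generator prior to subject recruitment". Research Design & Methods plans for 10 participants in each group and adds: "To account for attrition, 24 total subjects will be recruited; 12 per group". Each patient belongs to one group only, and time to ambulation is one value per patient.

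**Analysis.** Statistical Considerations specifies:

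- Aim 1: "A paired t-test will be used to evaluate time to ambulation in Group A as compared to Group B".
- Aim 3: "All hospital outcomes, except for discharge disposition, can be assessed between Group A and Group B by a paired t-test". The numeric outcomes are hospital, ICU, ECMO and ventilator days, plus time to ambulation, which is listed again there.
- As a general statement: "Test for normality will be completed via a paired t-test for parametric data and via Wilcoxon Rank Sum Test for non-parametric data".

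Aim 2 (functional outcomes) is assigned a repeated measures ANOVA and discharge disposition a chi-square test. No alpha, effect size, standard deviation or attrition rate is stated.

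**The concern.** A paired t-test analyses within-pair differences, so it needs a reason why a given Group A value belongs with a given Group B value. This design supplies none. The software will still run the test by taking the two columns row by row, so the pairing becomes an accident of how the file was laid out.

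Three consequences follow for Aim 1 and the numeric hospital outcomes:

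- The same data give different p-values in different row orders.
- The error degrees of freedom fall from the total sample size minus 2 to the number of pairs minus 1.
- Any patient without a row-mate is discarded, from a pilot of only 20 to 24 patients.

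The general sentence adds to the confusion. Neither the paired t-test nor the rank-sum test assesses normality. The rank-sum test is also for independent groups, so the two named tests do not belong to the same design.

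**Working it through.** **Inputs from the plan.** There are 10 per group, with 12 per group recruited. The arithmetic is coherent: 10 of 12 implies 2/12 = 16.7% attrition, and 10/(1 − 1/6) = 12 per group, or 24 in all. The rate itself is not stated.

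**Assumed inputs.** Two-sided 0.05; differences of 1.0 to 1.5 SD; attrition of 10% to 20%, independent in each arm.

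**1. Dependence on row order.** Take 10 v 10, SD 4 days in each arm and a difference of 3.5 days.

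- Two-sample: t = 3.5 / (4 × √(2/10)) = 3.5 / 1.789 = 1.957 on 18 df, so p = 0.066 in every order.
- Paired: with equal SDs, the standard error is 4 × √(2(1 − r)/10), where r is the correlation that the row order happens to create. At r = 0, t is again 1.957 but on 9 df, so p = 0.082. At r = −1 (one column reversed), the standard error is 8/√10 = 2.530 and t = 1.383, so p = 0.20. Once r exceeds about 0.25, p falls below 0.05.
- Over 100,000 random re-pairings of one such data set (normal scores, the second arm shifted by 3.5), the central 95% of paired p-values is about 0.01 to 0.16, and 24% are below 0.05.

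**2. Power.** With independent arms, the noncentrality is d/√(1/n1 + 1/n2) on n1 + n2 − 2 df for the two-sample test, and d/√(2/m) on m − 1 df for m arbitrary pairs. At d = 1.325, chosen because it gives the two-sample test 80% power at 10 v 10:

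| Completers | Two-sample: noncentrality, critical t, power | Paired: noncentrality, critical t, power | Patients dropped |
|---|---|---|---|
| 10 v 10 | 2.963, 2.101, 80% | 2.963, 2.262, 75% | 0 |
| 11 v 9 | 2.948, 2.101, 80% | 2.811, 2.306, 69% | 2 |
| 12 v 8 | 2.903, 2.101, 78% | 2.650, 2.365, 63% | 4 |

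Over d = 1.0 to 1.5 the loss is 4–5 points at 10 v 10, 9–10 at 11 v 9 and 14–16 at 12 v 8.

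**3. How often the arms end unequal.** Starting from 12 per arm, with completers binomial and independent:

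| Attrition | Arms unequal | Mean gap (patients dropped) | Gap of 4 or more |
|---|---|---|---|
| 10% | 72% | 1.1 | 2% |
| 15% | 77% | 1.4 | 4% |
| 20% | 80% | 1.5 | 7% |

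Equal arms are not always enough. If 2 of 12 rows are missing at random in each arm, the expected number of complete rows is 12 × (10/12) × (10/12) = 8.3, not 10.

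**4. Type I error.** In 200,000 null data sets with 10 per arm, random row order gives about 5% for normal data. If both columns were sorted by value, the rate would be 48% (36% for lognormal durations with log-SD 0.8).

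**The case against.** The strongest reply is that 'paired' is a slip. Both sentences describe a comparison between groups, and the non-parametric option named is an independent-groups test. The normality sentence may be a garbled attempt to say 't-test if normal, rank-sum if not'. That reading is plausible, but the word appears three times in the section and the paired test is the only one named for Aim 1. A slip in the specified analysis still has to be corrected.

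Several points on size stand:

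- If row order is unrelated to outcome, type I error stays near 5%. Nothing in the plan suggests sorted columns, so the 48% and 36% figures show only how far control could fail.
- Patients are dropped only if completer numbers differ or missing rows do not line up. Hospital outcomes come from the medical record, and data from before a withdrawal may be used, so losses may be smaller than assumed.
- At the planned 10 v 10 the power loss is only 4–5 points, and the 12 v 8 case is unlikely.
- The lowest paired p-values in the illustration owe something to its construction, because the two arms differ by an exact shift. The central range and the 24% are the figures to use.

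Scope also needs care. The Project Summary says "The primary aim of this study is to assess the functional impact of leg exercise during the pre-ambulation phase in patients undergoing ECMO", which points towards functional outcomes, but it then lists hospital measures, including time to ambulation, under the same aim. The ANOVA named for Aim 2 does not have this fault. That does not make the affected outcomes peripheral.

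**Conclusion.** The concern holds. The test named for Aim 1 and for the numeric Aim 3 outcomes does not fit a parallel-group design without matching, and it should be corrected before any analysis. The most certain harm is that the p-value is not unique: in the illustration, about a quarter of arbitrary row orders turn a two-sample p of 0.066 into a result below 0.05. Next is lost power, about 5 points if the arms finish equal and about 10 if they finish 11 v 9. An inflated type I error arises only if row order is related to outcome. The sizes rest on the assumed alpha, differences, SD and attrition. The mismatch between test and design rests on none of them.

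**What to change.** Edit three sentences in Statistical Considerations.

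- **Aim 1 and Aim 3:** replace the paired t-test with one independent-samples test, named in advance. The Wilcoxon rank-sum (Mann-Whitney) test is a reasonable choice, because the plan already names it and the outcomes are durations that are likely to be skewed. If a difference in means is wanted, name Welch's two-sample t-test instead. Either choice removes the fault; what matters is that only one is specified.
- **Normality sentence:** delete it.

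Both tests are available in SPSS, which the plan already uses. Patients and data collection are unaffected. This change does not settle how patients who die or never walk enter the time-to-ambulation analysis, which needs its own rule.

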10.0 Withdrawal of Participants

Please reference main protocol, section 13.0 pages 12-13 of 16

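### Time to first ambulation is to be compared by a paired t-test although the two groups are not paired, and the document gives no rule for patients who never walk

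*Combined protocol and SAP*

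**What the plan says.** The Statistical Considerations of the Project Proposal give one analysis for Aim 1: "A paired t-test will be used to evaluate time to ambulation in Group A as compared to Group B". The hospital outcomes list repeats the variable, "Length of time from physical therapy evaluation to initial ambulation", and the Aim 3 paragraph applies the same test: "All hospital outcomes, except for discharge disposition, can be assessed between Group A and Group B by a paired t-test". A rank test is also named, "via Wilcoxon Rank Sum Test for non-parametric data", but in a sentence about testing for normality, which neither named test does.

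Group assignment comes from a random sequence generated for 24 subjects (Recruitment and Consent). No matching or pairing is described. Recruitment is 12 per group to obtain 10, as an allowance for attrition. Participants "will participate over the duration of their ECMO treatment and hospitalization" (Research Design & Methods), so observation of walking ends when they leave hospital.

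On incomplete data, the text under Stopping Rules permits use of data collected before withdrawal. Section 10.0 otherwise says "Please reference main protocol, section 13.0 pages 12-13 of 16", and that section is not in the document. The nine disposition codes include transfer to another hospital but not death. No value, rank, censoring rule or competing-event rule is given for a patient who has not walked.

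**The concern.** There are two faults, and they differ in certainty.

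The first needs no assumption. A paired t-test works on within-pair differences. Here nothing defines a pair, so the analyst must match Group A rows to Group B rows by some arbitrary order, and the p-value follows from that order. If the arms supply unequal numbers of values, unmatched patients must also be discarded.

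The second is conditional on at least one patient not walking. Such a patient has no walking day. Dropping the patient compares only those who walked, a group formed after randomisation. Entering the day of leaving treats an early departure as early walking. Entering a late day such as Day 45 imposes a penalty that nobody has justified. If non-walking differs between arms, the estimate can be distorted in either direction, and a rule chosen after the data are seen could choose that direction. At stake is the pilot's estimate for its first aim.

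**Working it through.** **Inputs.** From the document: 12 recruited per group to obtain 10; data collection at Days 0, 5, 10, 15, 20, 30, 45 and discharge. It gives no alpha, effect size, SD or non-walking rate for this outcome, so there is no planned figure to reproduce. Everything below is illustrative and assumes a two-sided 5% level.

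**Example, 12 per arm.** Group B walking days: 4, 5, 6, 7, 8, 8, 9, 10, 12, 16, 24, 30 (sum 139). Each Group A day is 20% shorter (sum 0.8 × 139 = 111.2).

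*Everyone walks, unpaired test.* Means are 111.2/12 = 9.27 and 139/12 = 11.58, so A − B = −2.32 days. The SDs are 6.39 and 7.98 (pooled 7.23), so SE = 7.23 × √(2/12) = 2.95 and t = −0.785 on 22 df. This gives p = 0.44 and a 95% CI of −8.4 to +3.8 days.

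*Same data, paired test.* With both arms listed fastest to slowest, each difference is 20% of the B value: mean 2.32, SD 0.2 × 7.98 = 1.60, t = 2.32/(1.60/√12) = 5.0 in absolute value on 11 df, p = 0.0004. With one arm listed in the opposite order, p = 0.55. Only the row order changed.

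*The two slowest B patients (24 and 30) do not walk.*
- Dropped: the B mean is 85/10 = 8.50, so A − B = +0.77 days (A slower), p = 0.74, 95% CI −4.0 to +5.5.
- Exit day d entered for both: A − B = (111.2 − 85 − 2d)/12 = (26.2 − 2d)/12, which changes sign at d = 13.1.

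| Day entered | A − B (days) |
|---|---|
| 5 | +1.35 |
| 10 | +0.52 |
| 15 | −0.32 |
| 30 | −2.82 |
| 45 | −5.32 |

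- Ranked last: the probability that an A patient does better is 89.5/144 = 0.62, against 89/144 = 0.62 when everyone walks.

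*Only the slowest B patient does not walk.* Dropped: 9.27 − 109/11 = −0.64. With day d entered: (2.2 − d)/12, from −0.23 at Day 5 to −3.57 at Day 45. The sign holds and the size does not.

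*How often does dropping reverse the sign?* Losing one B patient: 0 of 12 cases. Losing two: 1 of 66, which is the case above. Losing three: 12 of 220. Losing two from each arm, which matches the attrition allowance: 188 of 4,356 (4.3%), and none when the same two are lost in both.

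**Simulation, 10 per arm.** Assumed: 70% walk at about day 8 (SD 3), 20% at about day 20 (SD 4), 10% never walk, and half the slow B patients also fail to walk. Non-walking is then 10% in A against 20% in B.
- Same walking speed in both arms: A looks 1.2 days slower if non-walkers are dropped, 0.3 slower if exit days of 5 to 30 are entered, and 2.4 faster if Day 45 is entered.
- A 20% faster: dropping gives A 1.0 day faster, against 2.15 when non-walking is 10% in both arms. About half the difference is lost, with no reversal on average.
- Mirror case, 20% in A and 10% in B at the same speed: dropping makes A look 1.2 days faster.
- No effect and equal non-walking: the unpaired t-test rejects in 4.9% of trials and the Wilcoxon test in 5.1%.

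A second model (12 per arm, exponential times, mean 10 against 20 days, 33% against 51% not walking) gave mean differences of −2.9, −3.2 and −8.0 days for dropping, exit day and Day 45. With no true difference, rejection stayed at 4 to 5%.

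**The case against.** Non-walking may be rare. Entry requires following commands, an active therapy referral and jugular veno-venous cannulation, and it excludes medical instability. Walking counts at any time in the hospital stay, not only on ECMO. The Project Summary's remark that results matter "particularly in those who are unable to engage in bipedal ambulation" fits patients who cannot walk yet, so it should not be read as saying that many never will. This stands, and it is why the second fault is conditional. Non-walking remains possible: participants are critically ill, therapy orders can be removed and transfer is a listed outcome.

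Recruiting 12 to obtain 10 suggests, without stating it, that losses will be dropped. It is not a non-walking rate, and dropping is the rule that conditions on having walked.

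The example is built so that B loses its slowest patients, and the 3.1-day shift (from −2.32 to +0.77) is about half of the 6.1-day half-width of the confidence interval. Both points are fair. A reader might infer that dropping non-walkers usually reverses the result or inflates false positives. The calculations do not support that: reversals are uncommon, and type I error stays near 5% when non-walking is equal.

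A reader might also infer that the trial has no withdrawal rule at all. That cannot be said, because section 10.0 points to main protocol text that is not in the document. Even so, a withdrawal rule would leave death, transfer and discharge before walking unaddressed.

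**Conclusion.** The concern holds in two parts.

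The paired test is wrong as written for two independently randomised groups. Confidence is high, and no assumption is needed. The p-values of 0.0004 and 0.55 are extremes from sorted listings of one example. They show that the result is arbitrary, not that it would usually be misleading.

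The missing rule for non-walkers makes the Aim 1 estimate ambiguous if any patient fails to walk. Confidence is moderate, because the document gives no rate and every size above rests on assumed walking times and losses. In the example with the two slowest B patients not walking, the estimate runs from 1.35 days slower to 5.32 days faster for Group A by choice of rule alone. With one such patient, the sign holds but the size still varies. If the same kinds of patients fail to walk in both arms, no systematic reversal follows.

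This should be fixed before data are seen. The consequence is a distorted or arbitrary pilot estimate, not a wrong sample size.

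**What to change.** In the Statistical Considerations, under Aim 1 and for the same variable under Aim 3, replace the paired t-test with one pre-stated analysis of all randomised patients in independent groups. Use the Wilcoxon rank-sum test, with all non-walkers, including deaths, ranked worse than every walker. Report the probability that a Group A patient does better, with its 95% CI, together with the number walking and the reasons for not walking by arm. Naming the rank test is not enough without the rank for non-walkers.

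State whether a withdrawn patient's walking date may be taken from the medical record, reconcile this with the main protocol's withdrawal section, and show results with and without withdrawals. Cumulative incidence of first ambulation with Gray's test, treating death and leaving hospital without walking as competing events, can be a sensitivity analysis. The plan names only SPSS, so check that the software can run it.

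The cost is analysis wording plus the date and reason for leaving without walking, including death, from records already being extracted. Sample size and visits do not change.

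There are downsides. The result is no longer a mean difference in days, and the rank order is a judgement. Power stays low, and it is slightly lower than for a walkers-only t-test when non-walking is equal. In simulation with 20% not walking in each arm and A 20% faster, the result was significant for A in 7.4% of trials against 9.9%, with the wrong sign in 28% against 21%. With 20% against 50% not walking and equal speed, the order reverses: 7.9% against 0.1% significant for A, and the wrong sign in 27% against 96%.

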- ECMO delivery is veno-venous with internal jugular catheter.

Exclusion Criteria

- Femoral catheter of any kind present.
- Veno-arterial ECMO setup.
- Sedation such that self-consent is not attainable.
- Medical instability, as determined by primary critical care physician.

Overview of Protocol for Aims 1-3:

Participants in either Group A (closed chain leg exercise group) or B (open chain exercise group) will progress through the established ECMO protocol led by their physical therapist. Participating therapists have extensive experience in working with patients on the Moveo who are in the ICU. Subjects will be assisted in the supine position from their bed to the Moveo device via a lateral transfer across a slide board to facilitate ease of movement.

Those in Group A will participate in leg exercise on the Moveo during item 4d of the ECMO protocol, whereby those in Group B will complete standard exercise as listed in item 4d. Group A participants will use the Moveo until subjective report of leg fatigue. Participants will self-select the pace of their leg exercise and the primary therapist will determine guidelines for percent of body weight lifted in accordance with standard practice physical therapy. Subjects will complete 1-4 sets of up to 25 reps of the squat exercise with 2 minutes of rest between each set. Subjects will receive physical therapy 5 days/week regardless of randomization into Group A or Group B.

Data Collection for Aims 1-3: Data will be collected on Day 0 (physical therapy evaluation day), Day 5, Day 10, Day 15, Day 20, Day 30, Day 45 (if applicable), and Day of discharge. Data collected will be categorized as specific to Aim 1 (time from initial physical therapy evaluation to initial ambulation), Aim 2 (functional outcomes) and Aim 3 (hospital outcomes). Recording of physiological data including heart rate (HR), blood pressure (BP), oxygen saturation (O2), and respiratory rate (RR) will be completed by trained physical therapists involved in the protocol at the onset of, and 1-minute post-conclusion of each therapy session. Therapy sessions are to be delivered at a frequency of five sessions per week.

- Functional Outcomes

- Leg strength as assessed by primary therapist via manual muscle test, using the Medical Research Council Sum Score (MRC Score)
- Grip strength, as assessed by hand dynamometer, completed by primary therapist

- 30-second sit to stand, completed by primary therapist

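### Aim 1 compares time to ambulation without adjusting for baseline leg strength; this gives up precision and leaves chance imbalance uncorrected, but does not bias the comparison

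*Combined protocol and SAP*

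**What the plan says.** - **Outcome.** Data Collection for Aims 1-3 defines "Aim 1 (time from initial physical therapy evaluation to initial ambulation").
- **Analysis.** Statistical Considerations, Aim 1: "A paired t-test will be used to evaluate time to ambulation in Group A as compared to Group B". No covariate, baseline adjustment or stratification is stated for Aim 1 there or elsewhere.
- **Prognostic factor.** The Project Summary says "The timeframe prior to mobilization depends on a number of factors, and can range significantly between different patient groups", and then "One such factor is strength".
- **Measurement.** The functional outcomes include "Leg strength as assessed by primary therapist via manual muscle test, using the Medical Research Council Sum Score (MRC Score"). The schedule reads "Data will be collected on Day 0 (physical therapy evaluation day), Day 5, Day 10, Day 15, Day 20, Day 30, Day 45", so strength is due on the day that starts the Aim 1 clock.
- **Use of Day 0 strength.** It enters the by-day comparisons ("Functional and Hospital outcomes will be analyzed to compare group differences at each of the data collection days") and the Aim 2 repeated measures ANOVA, but not Aim 1.
- **Allocation.** Recruitment and Consent (and section 9.2): "Group assignments will be determined based on 24 subjects, with the number 24 put into a random letter sequence generator prior to subject recruitment". Section 4.1 and the Data and Safety Monitoring Plan mention a randomization service. None of these places describes stratification.

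**The concern.** The protocol treats strength as something that affects how soon a patient mobilizes, and it tests an exercise meant to address weakness. It then analyses time to first ambulation as if nothing were known about how strong each patient was at the start. With 10 evaluable patients per arm, randomisation balances strength only loosely. If the arms start apart and strength predicts walking, part of the observed difference reflects where the arms started. The plan gives the analyst no response agreed in advance, and adjusting only after seeing an imbalance would be open to challenge. What is at stake is the precision and credibility of the first-listed aim.

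**Working it through.** **The plan's own figure.** Research Design & Methods gives 10 evaluable per group and 24 recruited (12 per group). Going from 20 to 24 implies attrition of 1 - 20/24 = 16.7%, or an inflation of 24/20 - 1 = 20%; neither rate is stated. There is no alpha, power, effect size or SD, so there is no power statement to reproduce.

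**Assumptions not in the documents.** Two-sided alpha 0.05; true difference 1 SD; normal, uncensored outcome; strength recorded for everyone; absolute correlation r between baseline strength and the outcome, varied because no value is given.

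**1. Chance imbalance.** The SE of the between-arm difference in mean strength is sqrt(2/n) SD.
- n = 10: SE = 0.447. P(difference above 0.5 SD in either direction) = 2[1 - Φ(0.5/0.447)] = 0.26.
- n = 12: SE = 0.408, probability 0.22.

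**2. Effect on the estimate.** A 0.5 SD imbalance moves the unadjusted estimate by r × 0.5 SD: 0.15, 0.25 and 0.35 SD at r = 0.3, 0.5 and 0.7.

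**3. Power with 10 per arm.**
- Unadjusted independent-groups t-test: noncentrality 1 × sqrt(10/2) = 2.236, 18 df, power 56%.
- Adjusted: divide the effect by f = sqrt[(1 - r²)(1 + 1/16)], where 16 = 2n - 4 allows for chance covariate imbalance, and use 17 df. At r = 0.5, f = sqrt(0.75 × 1.0625) = 0.893, noncentrality 2.236/0.893 = 2.505, power 66%.

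| r | Adjusted power (formula and simulation) |
|---|---|
| 0 | 53-54% |
| 0.25 | 56% (break-even) |
| 0.3 | 57-58% |
| 0.4 | 61% |
| 0.5 | 66% |
| 0.6 | 72-73% |

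With 12 per arm and r = 0.5, power goes from 65% to 75%.

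**4. Type I error.** Simulated with no true effect, it lay between 4.6% and 5.3% with and without adjustment. Among only those trials with an imbalance above 0.5 SD (10 per arm), the unadjusted test was falsely significant about 8/10/11% of the time at r = 0.4/0.5/0.6; the adjusted test stayed near 5%. The excess is offset in better balanced trials: at r = 0.5, (5% - 0.26 × 10%)/0.74 is about 3%.

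**5. Missing strength values.** If two patients per arm had no usable MRC (an assumption) and were dropped, the adjusted model on 8 per arm would have about 54% power at r = 0.5 and about 50% at r = 0.4. The unadjusted test on all 10 per arm has 56%. Complete-case adjustment would then cancel the gain.

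**The case against.** **The unadjusted comparison is already valid.** A reader might infer from step 2 that the planned comparison is biased, or cannot separate treatment from starting strength. The documents do not support that. Allocation is random, and a correct independent-groups interval already allows for chance imbalance. This stands: the loss is in precision and in how one unlucky trial can be read.

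**Strength may not be the main predictor.** The Project Summary calls it one among several factors, and the sentence before it concerns variation between patient groups. This trial enrols a narrowed group (veno-venous, jugular catheter, able to follow 3/3 commands). This also stands. If r is about 0.3 the gain is 1-2 points; below about 0.25 adjustment loses a little.

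**Baseline strength may not exist for everyone.** A reader might take the schedule to mean that a usable Day 0 value is in hand for each patient. It is only scheduled. Recruitment and Consent says most patients are at least partly sedated when therapy begins, manual muscle testing needs cooperation, and consent waits for 3/3 commands. Some Day 0 values may be missing or reflect sedation. This stands and shapes the fix. If consent comes late, the last value before allocation may be from Day 5 or later, after the Aim 1 clock has started. That may weaken it as a predictor, but because it precedes allocation it cannot be affected by the assigned arm.

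**Other defects come first.** The same sentence applies a paired test to two independent groups, and no rule covers patients who never walk. These are more serious, but correcting them would still leave strength unused.

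**Conclusion.** The point holds as one of efficiency and pre-specification. The plan names a factor, schedules its measurement, and leaves it out of the Aim 1 analysis. With 10 per arm there is about a one-in-four chance of a strength imbalance above 0.5 SD. Adjustment is worth about 10 points of power at a correlation of 0.5, 1-2 points at 0.3, and costs 2-3 points at zero. These figures rest on a 1 SD effect, an uncensored normal outcome and complete covariates, none of which the documents supply; deaths, patients who never walk, or missing MRC values would change them. The documents do not show bias, an inflated overall type I error, or that strength is the dominant predictor. The change is a cheap improvement that ranks behind correcting the Aim 1 test itself.

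**What to change.** First settle the Aim 1 model as an independent-groups or time-to-event analysis; do not attach a covariate to the paired t-test. Then write into Statistical Considerations, before any outcome data are seen:

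1. One covariate: the last scheduled MRC leg-strength value recorded before allocation. A cut-off at the first exercise session would admit values scored after allocation by the treating therapist, and no blinding is described.
2. A rule for a missing or unobtainable MRC that keeps every randomised patient in the model, for example single mean imputation of the baseline value without regard to group.
3. The unadjusted result reported beside the adjusted one, with a statement of which is the main result.

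Cost: a few sentences in the analysis plan and one degree of freedom in about 20 patients, which is roughly 2-3 points of power if strength does not predict walking. The gain shrinks if Day 0 MRC is often missing or unreliable because of sedation. Guaranteeing a cooperative reading before allocation would need an added assessment, which goes beyond a wording change. More than one covariate is not advisable at this sample size.
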